### **2.3.2 Benefit assessment**

Currently, there is one approved biologic therapy for the treatment of moderate to severe HS, adalimumab. But a substantial proportion of patients do not achieve clinical response with this therapy, and those who do often lose clinical response in a matter of a couple of years when they may require long-term treatment for this chronic disease. Existing options are limited including topical antibiotics, oral antibiotics, oral retinoids, and glucocorticoids. All these drugs are repurposed drugs with limited evidence supporting their efficacy and with considerable side-effects. There is a high unmet medical need in patients with moderate to severe HS.

Through combined TNF and OX40L inhibition, SAR442970 is expected to inhibit the recruitment of inflammatory cells such as neutrophils, B cells, and T cells, and downregulate effector mechanisms of T cells such as cytokine production observed in HS. Based on the mechanism of action, the potential benefits would be:

- Achievement of HiSCR50.
- Reduction in pain.
- Reduction in HS flares.
- Improvement in QoL.

### **2.3.3 Overall benefit/risk conclusion**

The clinical development program for SAR442970 is supported by the available nonclinical and clinical data and the potential benefit in the treatment of subjects with immune-mediated diseases. Hidradenitis suppurativa is characterized by a complex disease biology. Limited existing options for the treatment of HS include topical antibiotics, oral antibiotics, oral retinoids, and glucocorticoids. Blockade of several pathways in parallel through combined TNF and OX40L inhibition may confer greater benefit in terms of reduction of HS characteristic skin nodules and abscesses that lead to pain than any monotherapy.

SAR442970 was safe and well-tolerated in nonclinical toxicology studies and in clinical studies of healthy volunteers up to 300 mg given as a single dose and up to 150 mg given Q2W for 3 doses. Mitigation of the theoretical risks is possible through selection of appropriate study populations and monitoring in clinical trials.

Risk management procedures and specific safety monitoring will be implemented ([Section 2.3.1](#)). The design of the present study including selection criteria of the study population, risk mitigation strategy, and monitoring of safety variables, should maintain the positive balance regarding the expected risk/benefit ratio for SAR442970 in the treatment of participants with HS.

SAR442970 is still in clinical development and risks are not completely understood; however, based on the acceptable safety profile summarized above and the potential for considerable benefits on HS disease activity, on both acute episodes and on long-term sequelae, the potential benefits outweigh the risks in the proposed study population.

### 3 OBJECTIVES, ENDPOINTS, AND ESTIMANDS

**Table 2 - Objectives and endpoints**

| Objectives   | Endpoints  |
|--|--|
| Primary 

• To evaluate the efficacy of SAR442970 during the double-blind, placebo-controlled period in the biologic and small molecule immunosuppressive-naïve subgroup of participants with HS

  | 

• The clinical response as measured by the percentage of biologic and small molecule immunosuppressive-naïve participants achieving Hidradenitis Suppurativa Clinical Response (HiSCR50) (defined as ≥50% reduction from Baseline in the total abscess and inflammatory nodule [AN] count, with no increase from Baseline in abscess or draining tunnel count) at Week 16 (8, 9)

   |
| Secondary 

• To evaluate the efficacy and safety of SAR442970 in the biologic and small molecule immunosuppressive-naïve subgroup of participants with HS

• To evaluate the effect of SAR442970 on pain in the biologic and small molecule immunosuppressive-naïve subgroup of participants with HS

• To evaluate the pharmacokinetics (PK) of SAR442970 and anti-drug antibodies to SAR442970 in the biologic and small molecule immunosuppressive-naïve subgroup of participants with HS

 | 

• Time to onset of achieving HiSCR50

• Percentage of participants achieving HiSCR75 (defined as ≥75% reduction from Baseline in the total AN count, with no increase from Baseline in abscess or draining tunnel count) at Week 16

• Percentage of participants achieving HiSCR90 (defined as ≥90% reduction from Baseline in the total AN count, with no increase from Baseline in abscess or draining tunnel count) at Week 16

• Percentage of participants who experience improvement by at least one International Hidradenitis Suppurativa Severity Score System (IHS4) stage at Week 16 (See also Section 8.2.1.3 for definition of IHS4)

• Change in absolute score from Baseline in IHS4 at Week 16

• Percentage of participants who experience a flare, defined as at least a 25% increase in AN count (with a minimum increase of 2) relative to Baseline at Week 16 (See also Section 8.2.1.4 for definition of flare)

• Percentage of participants achieving IHS4-55 at Week 16 (defined as achievement of a 55% reduction in IHS4 score from Baseline)

• Incidence of treatment-emergent adverse events (TEAEs), adverse events of special interest (AESIs), and serious adverse events (SAEs) including local reactions

• Incidence of potentially clinically significant abnormalities in laboratory tests, vital signs, and electrocardiograms

• Percentage of participants achieving at least 30% reduction and at least 1 unit reduction from Baseline in weekly average of daily [REDACTED]
[REDACTED]
[REDACTED]
[REDACTED]
[REDACTED]

• Serum SAR442970 concentrations throughout the study

• Incidence of anti-SAR442970 antibody positive response throughout the study

 |

Forest plot showing the effect of interventions on various endpoints. The y-axis lists endpoints: DLQI, DLQI  $\geq 4$ , and various clinical outcomes. The x-axis shows the effect size (mean difference) for each intervention. Interventions are grouped by color: blue, green, red, and black. Horizontal lines indicate the 95% confidence interval for each intervention.

| Endpoint                       | Intervention 1 (Blue) | Intervention 2 (Green) | Intervention 3 (Red) | Intervention 4 (Black) |
|--------------------------------|-----------------------|------------------------|----------------------|------------------------|
| DLQI                           | 0.5                   | 0.8                    | 0.6                  | 0.7                    |
| DLQI $\geq 4$                  | 0.3                   | 0.5                    | 0.4                  | 0.6                    |
| Shortness of breath            | 0.2                   | 0.3                    | 0.2                  | 0.4                    |
| Wheezing                       | 0.1                   | 0.2                    | 0.1                  | 0.3                    |
| Cough                          | 0.1                   | 0.2                    | 0.1                  | 0.2                    |
| Exercise tolerance             | 0.2                   | 0.3                    | 0.2                  | 0.4                    |
| Overall quality of life        | 0.2                   | 0.3                    | 0.2                  | 0.4                    |
| Health related quality of life | 0.2                   | 0.3                    | 0.2                  | 0.4                    |
| Work                           | 0.1                   | 0.2                    | 0.1                  | 0.3                    |
| Respiratory symptoms           | 0.1                   | 0.2                    | 0.1                  | 0.2                    |
| Health status                  | 0.1                   | 0.2                    | 0.1                  | 0.2                    |
| Daytime symptoms               | 0.1                   | 0.2                    | 0.1                  | 0.2                    |
| Exercise                       | 0.1                   | 0.2                    | 0.1                  | 0.2                    |
| Overall                        | 0.2                   | 0.3                    | 0.2                  | 0.4                    |

Primary estimand defined for primary efficacy endpoint is summarized in [Table 3](#). More details are provided in [Section 9.2](#).

For all these estimands, the comparison of interest will be the comparison of SAR442970 vs placebo.

**Table 3 - Summary of primary estimands for the primary endpoint**

| Endpoint Category   | Endpoint  | Population   | Estimands   |  | Population-level summary (Analysis and missing data handling) |
|---|---|--|---|--|---|
|   |   |  | Intercurrent event(s) handling strategy   |  |   |
| Primary objective: To evaluate the efficacy of SAR442970 during the double-blind, placebo-controlled period in the primary analysis population of the biologic and small molecule immunosuppressive-naïve subgroup participants with moderate to severe HS |   |  |   |  |   |
| Primary endpoint  | Percentage of participants achieving HiSCR50 at Week 16 | Biologic and small molecule immunosuppressive-naïve population | 
The following intercurrent events will be handled with the composite strategy; participants will be considered as non-responders after such IE.
 
 
Starting or increase in dose of oral antibiotic therapy during the treatment period.
 
Starting selected prohibited medications. Please refer to Section 6.9.1. Further details of selection will be specified in the SAP.
 
Discontinuation of study intervention due to lack of efficacy. The following IEs will be handled with the treatment policy strategy (without IEs that need to be handled with composite strategy). Data collected after starting such IE will be included.
 
Starting other prohibited medications.
 
Discontinuation of study intervention due to reasons other than lack of efficacy.
 
 | 
Bayesian logistic regression model including treatment group and adjusted by randomization stratum (Hurley Stage). The statistical analysis will be conducted following a Bayesian approach using an informative prior on the placebo response rate based on the historical studies available. Missing data will be imputed as non-responder.
 |   |

Abbreviations: HiSCR50=hidradenitis suppurativa clinical response; IE=intercurrent event; SAP=statistical analysis plan.

### 3.1 APPROPRIATENESS OF MEASUREMENTS

All efficacy measurements in this study are standard for assessing disease activity in participants with HS. The HiSCR50 and IHS4 have been validated in HS and extensively used. The HiSCR50 is widely accepted by health authorities as the basis supporting marketing authorization of adalimumab for patients with HS. The HiSCR75, HiSCR90, and flare rate are also routinely assessed in HS clinical studies because efficacy of SAR442970 may have an impact on these

derivations of the data used to calculate the HiSCR50. Pain is a common comorbid symptom in patients with HS and will be assessed by the [REDACTED]. Occurrence of TEAEs, SAEs, AESI, and PCSAs for vital signs, ECGs, and clinical laboratory assessments are standard measures to characterize safety and tolerability of therapeutic agents in clinical trials. Serum SAR442970 concentrations are the appropriate measures to quantify the PK profile of SAR442970 and support exposure-response analyses. Because SAR442970 is a large protein it may induce the formation of ADA, which may have the potential to impact efficacy or safety.

## 4 STUDY DESIGN

### 4.1 OVERALL DESIGN

This is a multinational, multi-center, randomized, double-blind, placebo-controlled, Phase 2a proof-of-concept study to evaluate the efficacy and safety of SAR442970 in adult participants with moderate to severe HS.

The intervention in the study includes up to 14 total doses of IMP administration Q2W to complete up to 28 weeks of treatment with SAR442970.

The target population of the study is participants with HS based on a history of signs and symptoms consistent with HS for at least 1 year prior to Baseline and demonstrating moderate to severe disease at Baseline as defined by HS lesions present in at least 2 distinct anatomic areas (eg, left and right axilla; or left axilla and left inguino-crural fold), one of which must be Hurley Stage II or Hurley Stage III, an abscess and inflammatory nodule (AN) count of  $\geq 3$ , a draining tunnel count  $\leq 20$ , and CRP level of  $> 3$  mg/L.

Additionally, all participants must have had an inadequate response to a course of an oral antibiotic for treatment of HS or exhibited recurrence after discontinuation of antibiotics or demonstrated intolerance to antibiotics or have a contraindication to oral antibiotics for treatment of their HS as assessed by the Investigator through participant interview and review of medical history. Participants will be considered to have had an inadequate response or loss of response to oral antibiotics if at least 1 of the following occurs while receiving antibiotics:

- Progression of Hurley Stage (ie, the Hurley Stage of at least one affected anatomic region progressed from I→II, II→III, or I→III).
- Participant required at least one intervention (eg, I&D or intralesional injection of corticosteroid).
- Participant experienced pain interfering with activities of daily living, with unsatisfactory relief from over-the-counter analgesics (eg, ibuprofen or acetaminophen).
- Participant experienced pain requiring opioids, including tramadol.
- Participant experienced drainage interfering with activities of daily living (eg, requires multiple dressing changes and/or changes of clothes daily).
- Participant experienced an increase in the number of anatomic regions affected by HS.
- Participant experienced at least one new abscess or one new draining fistula.
- Participant experienced a flare (or worsening of disease) as determined by the Investigator while on oral antibiotics.

Participants will be considered as intolerant to oral antibiotic when oral antibiotic therapy has been discontinued as a result of a significant adverse reaction to oral antibiotic administration. A reaction will be considered significant if the adverse reaction is at least moderate (ie, the adverse event causes the subject discomfort or interrupts the participant's usual activities or function) as assessed by the Investigator through participant interview and review of medical history.

Examples of significant adverse reactions include, but are not limited to:

- Nausea resulting in decreased oral intake.
- Dizziness/disequilibrium/lightheadedness/vertigo interfering with normal function.
- Hypersensitivity reactions including, but not limited to, rash, flushing, urticaria, dyspnea, or drug fever  $\geq 38^{\circ}\text{C}$ .
- Diarrhea manifesting as an increase in stool frequency of at least 4 stools per day over participant's baseline.

Approximately 84 participants will be randomized in a 2:1 ratio to SAR442970 150 mg or matching placebo. Randomization will first be stratified by HS treatment history into 2 major subgroups:

- Biologic and small molecule immunosuppressive-naïve subgroup.
- TNF-experienced subgroup.

The biologic and small molecule immunosuppressive-naïve subgroup is composed of participants who have never received biologic therapies, such as anti-TNF therapy, anti-IL17, anti-IL1, anti-IL36, or anti-IL23, or small molecule immunosuppressive therapies, such as JAK/TYK inhibitors. The recruitment target for the biologic and small molecule immunosuppressive-naïve subgroup is approximately 66 participants. Randomization will be further stratified by Hurley Stage (II or III). Within the biologic and small molecule immunosuppressive-naïve subgroup, the number of participants with Hurley Stage III is not to exceed more than 50% in order to recruit a population with the desired disease severity.

The TNF-experienced subgroup is composed of participants who experienced at least one of the following scenarios after receiving a single anti-TNF therapy (adalimumab, certolizumab pegol, etanercept, golimumab, infliximab, etc) for at least 12 weeks as assessed by the Investigator through participant interview and review of medical history:

- Participants who had a complete response to anti-TNF therapy for HS per Investigator discretion and subsequently lost response, or
- Participants who had a partial response to anti-TNF therapy for HS per Investigator discretion, or
- Participants who did not achieve a partial response to anti-TNF therapy for HS per Investigator discretion, or
- Participants who stopped using anti-TNF therapy due to reasons other than an AE (ie, insurance or access or reasons) (8, 9).

For the TNF-experienced subgroup, if participants have received more than 1 anti-TNF therapy for HS, they are not eligible for participation. Participants that have experienced an AE related to anti-TNF therapy (examples include, but are not limited to, serum sickness or anaphylaxis) that would contraindicate re-administration of an anti-TNF class therapy will be excluded. The recruitment target for the TNF-experienced subgroup is approximately 18 participants. Randomization will be further stratified by Hurley Stage (II or III). Within the TNF-experienced subgroup, the number of participants with Hurley Stage III is not to exceed more than 50%.

The primary analysis population is the biologic and small molecule immunosuppressive-naïve subgroup. Efficacy objectives and endpoints will be evaluated in an exploratory manner in the TNF-experienced subgroup.

All participants will have a Screening Period of up to 4 weeks to assess eligibility, a treatment period of up to 28 weeks, and an 8-week safety Follow-up Period. Period A is a 16-week double-blind, placebo-controlled period. Period B is an open-label period that may last up to 12 weeks depending on the individual participant. Period C will commence with an EOT visit and conclude with an EOS Visit. All participants from Period A will proceed to Period B and will be receiving SAR442970 150 mg. After completion of Period A and Period B, all participants will proceed to Period C, an 8-week safety Follow-up Period (For participants in the US, response will be assessed at the Week 20 visit. Response will be defined as  $\geq 50\%$  reduction from Baseline in the total AN count, with no increase from Baseline in abscess or draining tunnel count at Week 20. Responders at Week 20 will continue in Period B to complete the 12-week open-label period. Non-responders at Week 20 will move directly to the safety follow-up period with the Week 20 visit serving as their EOT visit).

During the Screening Period, upon confirmation of eligibility based on inclusion and exclusion criteria, a washout of prohibited medications should be performed if necessary.

During the 28-week Treatment Period (Period A and Period B), on-site visits will be performed every 2 weeks. During the 8-week safety Follow-up Period (Period C), one on-site visit will be performed at the EOS visit. For all visits, participants will undergo all assessments specified in the schedule of activities (SoA), such as physical and/or clinical laboratory examinations, disease specific QoL measurements, and HS clinical parameters.

The primary objective of the study is to evaluate the efficacy of SAR442970 compared to matching placebo in biologic and small molecule immunosuppressive-naïve participants based on the percentage of participants who achieve clinical response at Week 16 by the HiSCR50 (defined as  $\geq 50\%$  reduction from Baseline in the total AN count, with no increase from Baseline in abscess or draining tunnel count). The secondary endpoints include HiSCR75, HiSCR90, International Hidradenitis Suppurativa Severity Score (IHS4), safety and tolerability, Hidradenitis Suppurativa Skin Pain Numeric Rating Scale, PK, and formation of ADA. The key objective of Period B is to evaluate the maintenance of response in Week 16 HiSCR50 responders at Week 28, the depth of response based on achievement of HiSCR75 and HiSCR90 during Period B, and breadth of response based on the rate of conversion of partial responders (defined as  $\geq 25\%$  reduction from Baseline in the total abscess and inflammatory nodule count, with no increase from Baseline in abscess or draining tunnel count) at Week 16 to HiSCR50 responders at Week 28 in biologic and small molecule immunosuppressive-naïve participants in an exploratory manner. Period C is a safety Follow-up Period. Efficacy objectives and endpoints will be evaluated in an exploratory manner in TNF-experienced participants. Safety, PK, PD, and immunogenicity assessments will be evaluated in both biologic and small molecule immunosuppressive-naïve and TNF-experienced participants.

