### **8.2.1.2 *Hidradenitis Suppurativa Clinical Response***

The Hidradenitis Suppurativa Clinical Response (HiSCR50) is a valid and meaningful endpoint for assessing HS treatment effectiveness in controlling inflammatory manifestations in this population (8). The HiSCR50 is defined as at least a 50% reduction from Baseline in the total abscess and inflammatory nodule count, with no increase from Baseline in abscess or draining tunnel count.

The HiSCR75 is defined as at least a 75% reduction from Baseline in the total abscess and inflammatory nodule count, with no increase from Baseline in abscess or draining tunnel count. The HiSCR90 is defined as at least a 90% reduction from Baseline in the total abscess and inflammatory nodule count, with no increase from Baseline in abscess or draining tunnel count.

The HiSCR50, HiSCR75, and HiSCR90 will be assessed at each of the prespecified times when the HS Clinical Parameters are scheduled to be assessed, at the designated study visits according to the SoA (see [Section 1.3](#)). The score will be calculated using data recorded for HS Clinical Parameters in the eCRF (see [Section 8.2.1.1](#)).

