**Table 10 - Accuracy of the 80% credible interval in the biologic and small molecule immunosuppressive-naïve population**

| SAR442970
incidence rate (n) | Placebo rate
(n) | Lower limit | Upper limit | Half-width |
|---------------------------------|---------------------|-------------|-------------|------------|
|                                 |                     |             |             |            |

A sample size of 66 participants randomized in a █ ratio to SAR442970 versus placebo will provide a half-width for the 80% credible interval of less than 0.145 which is deemed sufficient.

For TNF-experienced population, an informative prior distribution for the placebo group HiSCR50 rate has been chosen as a beta distribution with parameter (████). This prior distribution contributes an approximate effective sample size of 2 participants for the placebo treatment group. Sample size calculations were performed to ensure reasonable accuracy for the estimation of the response rate. █████

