2.5 EXPLORATORY EFFICACY ENDPOINT(S) ANALYSIS OF PERIOD B

The analysis of exploratory efficacy endpoints of Period B (See [Table 2](#) above) will be only descriptive. The general consideration defined in [Section 2.1](#) will be applied and no statistical testing will be implemented.

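### Protocol 4.1 defines Week 16 partial responders by a lower limit only, so read literally the Period B conversion rate also counts participants who are already HiSCR50 responders

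*Protocol*

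**What the plan says.** Protocol 4.1 lists three parts to the key objective of Period B, all to be evaluated in an exploratory manner.

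- Maintenance: "to evaluate the maintenance of response in Week 16 HiSCR50 responders at Week 28".
- Depth: achievement of HiSCR75 and HiSCR90 during Period B.
- Breadth: "breadth of response based on the rate of conversion of partial responders" "at Week 16 to HiSCR50 responders at Week 28 in biologic and small molecule immunosuppressive-naïve participants".

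A parenthesis in the same sentence defines the partial responder as having at least a 25% "reduction from Baseline in the total abscess and inflammatory nodule count, with no increase from Baseline in abscess or draining tunnel count". It gives no upper limit and does not exclude HiSCR50 responders.

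Protocol 8.2.1.2 uses the same form for the response itself: "The HiSCR50 is defined as at least a 50% reduction from Baseline in the total abscess and inflammatory nodule count", again with no increase in abscess or draining tunnel count.

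SAP 2.5 refers to SAP Table 2 for the Period B exploratory endpoints. It says the analysis is descriptive and that "no statistical testing will be implemented". The exploratory rows of SAP Table 2 are largely redacted, and those of Protocol Table 2 cannot be read in the public copy. No readable text in either document sets an upper bound.

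**The concern.** The breadth measure is meant to show whether longer treatment turns incomplete responders into responders. Under the stated definition, a participant who is already a HiSCR50 responder at Week 16 enters the denominator and counts as a conversion by staying where they were. The whole maintenance denominator then sits inside the breadth denominator, and the two objectives no longer measure different things.

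Because the analysis is descriptive, the percentage is itself the result. No test or comparison would expose a denominator that mixes two groups. A high figure could appear even if few participants with a 25% to <50% reduction improved further.

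**Working it through.** **No figure to reproduce.** The documents state no expected conversion rate and no sample size for this endpoint.

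**Step 1: is HiSCR50 nested inside partial response?** The abscess and tunnel conditions are identical, so only the AN threshold differs. Inclusion criterion I 06 allows a Baseline AN count from 3.

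| Baseline AN | Week 16 counts with ≥25% reduction | Counts with ≥50% reduction | Counts that are partial only |
|---|---|---|---|
| 3 | 0–2 | 0–1 | 2 |
| 4 | 0–3 | 0–2 | 3 |
| 10 | 0–7 | 0–5 | 6–7 |
| 20 | 0–15 | 0–10 | 11–15 |

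The ≥50% set always lies inside the ≥25% set. At low Baseline counts a single value is truly partial.

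**Step 2: effect on the rate.** Let R be the number of Week 16 HiSCR50 responders, P the number with a 25% to <50% reduction (and no increase in abscesses or draining tunnels), m the share of R still HiSCR50 at Week 28, and c the share of P who reach HiSCR50 at Week 28.

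- Rate as worded: (R·m + P·c)/(R + P)
- Rate with the bound: c
- Difference: [R/(R + P)] × (m − c)

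**Step 3: inputs.**

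- Naïve subgroup 66, randomized 2:1, so 44 and 22 (Protocol 4.1 and 9.5).
- Placebo HiSCR50 rate 30%, the mean of the Beta(2.1; 4.9) prior, 2.1/7.0 (SAP 2.2.2).
- HiSCR50 rate on SAR442970 42% or 59%. These are the rates in the two Phase 3 adalimumab trials described in Protocol 2.1.1; using them for SAR442970 is an assumption.
- P at 10%, 15% or 20% of 66; m at 60%, 75% or 90%; c at 20%, 35% or 50%. All are assumptions, with no source in the documents.

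**Step 4: one case.** Active rate 42%, P = 15%, m = 75%, c = 35%.

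- R = 44 × 0.42 + 22 × 0.30 = 18.48 + 6.60 = 25.08
- P = 0.15 × 66 = 9.9
- As worded: (25.08 × 0.75 + 9.9 × 0.35)/34.98 = (18.81 + 3.465)/34.98 = 0.637, or 64%
- With the bound: 35%
- Difference: (25.08/34.98) × 0.40 = 0.287, about 29 points

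SAP 2.1 presents Period B by original arm as well as overall. For the 44 who start on SAR442970, with R = 18.48 and P = 6.6, the rate as worded is (13.86 + 2.31)/25.08 = 0.645, much the same.

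**Step 5: range.**

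- Smallest gap: active 42%, P = 20%, m = 60%, c = 50%. (25.08/38.28) × 0.10 = 0.066, about 7 points.
- Largest gap: active 59%, so R = 44 × 0.59 + 6.60 = 32.56, with P = 10%, m = 90%, c = 20%. (32.56/39.16) × 0.70 = 0.582, about 58 points.
- Across the grid, participants already at HiSCR50 make up 66% to 83% of the denominator as worded.

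The gap is zero if m = c and negative if m < c. The calculation treats every participant as having a Week 28 result. It ignores the rule that US participants not in response at Week 20 leave Period B.

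**The case against.** The strongest reply is that Protocol 4.1 is a narrative summary and the operative endpoint belongs in the objectives tables. Their exploratory rows cannot be read, and text lost to redaction is not missing from the plan. This stands. A reader might infer that the planned analysis will in fact count HiSCR50 responders as converted. The documents do not show that; they show that the one readable definition has no ceiling.

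The second reply is that the sentence explains itself. One cannot convert to a status already held, and Week 16 HiSCR50 responders already have their own objective. This is good evidence that 25% to <50% was intended. It does not change the definition in the parenthesis, which is what a programmer would apply if the tables repeat it.

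The third reply is that the size is illustrative. R rests on borrowed rates, and P, m and c are assumed, so inflation is conditional on maintenance exceeding conversion. That also stands. If the maintenance numerator and denominator were both reported, a reader aware of the overlap could recover the bounded rate by subtraction.

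Finally, a reader might infer that this rate feeds a development decision. The text on planning future development, in Protocol 9.3, concerns an optional interim analysis during Period A. SAP 2.9 says none is planned. Nothing readable ties the Week 28 conversion rate to such a decision.

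**Conclusion.** The point holds as a flaw in the readable definition. As worded in Protocol 4.1, partial responders include all Week 16 HiSCR50 responders, and the conversion rate mixes maintenance with conversion. On the assumptions shown it overstates true conversion by about 7 to 58 points, with 64% against 35% as a middle case. The direction depends on maintenance being higher than conversion, which is likely but not documented. Whether the error reaches the analysis depends on endpoint rows that cannot be read.

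The consequence is confined to an exploratory, descriptive measure. The primary and secondary endpoints and the sample size are untouched. It still merits correction because the measure is part of the named key objective of Period B and the stated rule, if applied, gives a figure that does not answer the question asked.

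**What to change.** In Protocol 4.1, define a Week 16 partial responder as having at least a 25% but less than a 50% reduction from Baseline in AN count, with no increase from Baseline in abscess or draining tunnel count; that is, not a HiSCR50 responder at Week 16. Make the same change in Protocol Table 2 and SAP Table 2 if they carry the open-ended wording. On lesion counts the <50% bound is sufficient: a participant with a larger AN reduction but more abscesses or draining tunnels fails both definitions.

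The SAP should also state the denominator, including how US participants who leave at Week 20 without a Week 28 assessment are counted.

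The cost is a few words. No visit, assessment or data item changes, because the lesion counts are already collected. The downside is a smaller denominator, hence a less precise rate, and probably a less favourable figure.
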